BSA	Proportion of patients with $\leq 1\%$ of BSA with psoriasis involvement	CMH analysis with NRI	ITT	All scheduled visits in Induction Period; All scheduled visits in Induction and Maintenance Periods
	BSA change from baseline	MMRM; ANCOVA with mBOCF	ITT	All scheduled visits in Induction Period; All scheduled visits in Induction and Maintenance Periods
PSS	PSS Symptoms Score of 0; PSS Signs Score of 0	CMH analysis with NRI	ITT - Patients with Baseline PSS Symptoms Score ≥ 1 and PSS Signs Score ≥ 1 , respectively	All scheduled weeks in Induction Period; All scheduled weeks/visits in Induction and Maintenance Periods
	Change from baseline for PSS Symptoms Score, Signs Score, and Item Scores	MMRM; ANCOVA with mBOCF	ITT	All scheduled weeks in Induction Period; All scheduled weeks/visits in Induction and Maintenance Periods
PSSI	PSSI change from baseline	MMRM; ANCOVA with mBOCF	ITT - Patients with Scalp Involvement at Baseline	All scheduled visits in Induction Period; All scheduled visits in Induction and Maintenance Periods
	PSSI score = 0	CMH analysis with NRI	ITT - Patients with Scalp Involvement at Baseline	All scheduled visits in Induction Period; All scheduled visits in Induction and Maintenance Periods
PPASI	PPASI change from baseline	MMRM; ANCOVA with mBOCF	ITT - Patients with Palmoplantar Involvement at Baseline	All scheduled visits in Induction Period; All scheduled visits in Induction and Maintenance Periods
	PPASI 50; PPASI 75; PPASI 100;	CMH analysis with NRI	ITT - Patients with Palmoplantar Involvement at Baseline	All scheduled visits in Induction Period; All scheduled visits in Induction and Maintenance Periods
NAPSI	NAPSI change from baseline	MMRM; ANCOVA with mBOCF	ITT - Patients with Nail Psoriasis Involvement at Baseline	All scheduled visits in Induction Period; All scheduled visits in Induction and Maintenance Periods

Description of Efficacy/Health Outcomes Analyses

Measure	Variable	Analysis Method (Section 6.1.2)	Population (Section 6.1.1)	Time Point and Period
NAPSI	NAPSI score = 0	CMH analysis with NRI	ITT - Patients with Nail Psoriasis Involvement at Baseline	All scheduled visits in Induction Period; All scheduled visits in Induction and Maintenance Periods
DLQI	DLQI (0,1) and ≥ 5 -point reduction from baseline	CMH analysis with NRI	ITT - Patients with Baseline DLQI ≥ 5	All scheduled visits in Induction Period; All scheduled visits in Induction and Maintenance Periods
	DLQI (0,1)	CMH analysis with NRI	ITT - Patients with Baseline DLQI > 1	All scheduled visits in Induction Period; All scheduled visits in Induction and Maintenance Periods
	DLQI total score ≥ 5 -point reduction from baseline	CMH analysis with NRI	ITT - Patients with Baseline DLQI ≥ 5	All scheduled visits in Induction Period; All scheduled visits in Induction and Maintenance Periods
	DLQI total score and domain scores change from baseline	MMRM; ANCOVA with mBOCF	ITT	All scheduled visits in Induction Period; All scheduled visits in Induction and Maintenance Periods
SF-36	SF-36 change from baseline for PCS and MCS Component Scores and Domain Scores	ANCOVA with mBOCF	ITT	Last visit in Induction Period
		MMRM; ANCOVA with mBOCF	ITT	All scheduled visits in Induction and Maintenance Periods
	SF-36 PCS Responder Definition; SF-36 MCS Responder Definition; SF-36 Domain score Responder Definition;	CMH analysis with NRI	ITT	Last visit in Induction Period; All scheduled visits in Induction and Maintenance Periods
PatGA	PatGA(0)	CMH analysis with NRI	ITT - Patients with Baseline PatGA > 0	All scheduled visits in Induction Period; All scheduled visits in Induction and Maintenance Periods
	PatGA (0,1) and ≥ 2 -point improvement from baseline	CMH analysis with NRI	ITT - Patients with Baseline PatGA ≥ 2	All scheduled visits in Induction Period; All scheduled visits in Induction and Maintenance Periods
WPAI-PSO	Change from baseline in WPAI-PSO Scores (Absenteeism, Presenteeism, Work Productivity, Activity Impairment)	ANCOVA with mBOCF	ITT - Patients with Baseline Employment Status of Yes	Last visit in Induction Period
		MMRM; ANCOVA with mBOCF	ITT - Patients with Baseline Employment Status of Yes	All scheduled visits in Induction and Maintenance Periods

Description of Efficacy/Health Outcomes Analyses

Measure	Variable	Analysis Method (Section 6.1.2)	Population (Section 6.1.1)	Time Point and Period
TSQM	Mean Effectiveness, Convenience, and Global Satisfaction	ANCOVA with mBOCF	ITT	Last visit in Induction Period
		MMRM; ANCOVA with mBOCF	ITT	All scheduled visits in Induction and Maintenance Periods
EQ-5D-5L + Bolt On	Change from baseline of EQ-5D VAS and Index scores	MMRM; ANCOVA with mBOCF	ITT	All scheduled visits in Induction Period; All scheduled visits in Induction and Maintenance Periods
	EQ-5D Dimension Scores with no problems	CMH analysis with NRI	ITT	All scheduled visits in Induction Period; All scheduled visits in Induction and Maintenance Periods
QIDS-SR16	QIDS-SR16 Response; QIDS-SR16 Remission	CMH analysis with NRI	ITT - Patients with Baseline Value ≥ 11	Last visit in Induction Period; All scheduled visits in Induction and Maintenance Periods
Facial Psoriasis	Facial Psoriasis	Summary statistics; Shift table	ITT	Last visit in Induction Period; All scheduled visits in Induction and Maintenance Periods
	Absence of Facial Psoriasis	CMH analysis with NRI	ITT - Patients with Baseline Facial Psoriasis	Last visit in Induction Period; All scheduled visits in Induction and Maintenance Periods

Abbreviations: AUC = area under the curve; ANCOVA = analysis of covariance; BSA = body surface area; CMH = Cochran-Mantel-Haenszel; DLQI = Global Assessment Dermatology Life Quality Index; E5-5D = EuroQoL 5 Dimensions; EQ-5D-5L = EuroQoL-5 Dimensions-5 Level; ITT = intent-to-treat; KM = Kaplan-Meier; mBOCF = modified baseline observation carried forward; MCS = Mental Component Score; MMRM = mixed model repeating measures; NAPSI = Nail Psoriasis Severity Index; NRI = nonresponder imputation; PASI = Psoriasis Area and Severity Index; PASI 75/90/100 = $\geq 75\%$ / $\geq 90\%$ / $\geq 100\%$ improvement in PASI from baseline; PatGA = Patients Global Assessment of Psoriasis; PCS = Physical Component Score; PPASI = Palmoplantar Psoriasis Severity Index; PPS = per protocol set; PSS = Psoriasis Symptoms Scale; PSSI = Psoriasis Scalp Severity Index; QIDS-SR16 = a self-administered, 16-item instrument to assess symptoms of depression; SF-36 = a 36-item, patient-completed measure designed to assess health; sPGA = Static Physician Global Assessment; TSQM = Treatment Satisfaction Questionnaire for Medication; WPAI-PSO = Work Productivity and Activity Impairment - Psoriasis.

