
Other Secondary^b
 
To assess whether mirikizumab induction dosing is superior to placebo with respect to an early, clinically meaningful response
 
To compare mirikizumab to placebo with respect to clinical response and time to clinical response during the induction dosing period, and with respect to patient-reported outcomes during the induction dosing period
	
At Week 4:
 
 • Proportion of patients achieving PASI 75 
At Week 16 and various time points over the first 16 weeks of dosing:
 
 • Proportion of patients achieving PASI 90 • Change from baseline in PPASI total score in patients with palmoplantar involvement at baseline • Change in PSSI total score in patients with scalp involvement at baseline • Change from baseline in NAPSI total score in patients with fingernail involvement at baseline • Change from baseline on the SF-36 physical component summary (PCS) and mental component summary (MCS) • Change from baseline on PatGA of disease severity** • Change from baseline for the WPAI PSO scores (Absenteeism, Presenteeism, Work Productivity Loss, and Activity Impairment) • Change from baseline in QIDS-SR16 total score in those with a baseline QIDS-SR16 total score ≥ 11 • Proportion of patients achieving a DLQI total score of (0,1) with at least a 5-point improvement (reduction) from baseline in patients with a baseline DLQI total score ≥ 5 • Proportion of patients achieving DLQI (0,1) with DLQI baseline score > 1

Protocol-Defined Objectives and Endpoints

Objectives	Endpoints

To compare mirikizumab to secukinumab with respect to clinical response and time to clinical response during the induction dosing period, and with respect to patient-reported outcomes during the induction dosing period
 
To assess whether 250-mg mirikizumab Q8W and 125-mg mirikizumab Q8W maintenance dosing is noninferior to secukinumab with respect to high levels of clinical response
	
At Week 16 and various time points over the first 16 weeks of dosing:
 
 • Proportion of patients achieving PASI 90 
At Week 24:
 
 • Proportion of patients achieving PASI 90 
At Week 52:
 
 • Proportion of patients achieving an sPGA (0)

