NAPSI	Nail Psoriasis Severity Index (NAPSI): in patient with baseline fingernail psoriasis involvement, NAPSI will be used to evaluate the severity of fingernail bed psoriasis and fingernail matrix psoriasis by area of involvement in the fingernail unit. The fingernail is divided with imaginary horizontal and longitudinal lines into quadrants. Each fingernail is given a score for fingernail bed psoriasis (0-4) and fingernail matrix psoriasis (0-4), depending on the presence (score of 1) or absence (score of 0) of any of the features of fingernail bed and fingernail matrix psoriasis in each quadrant: 0 = none 1 = present in 1 quadrant of nail 2 = present in 2 quadrants of nail 3 = present in 3 quadrants of nail 4 = present in 4 quadrants of nail	NAPSI score change from baseline	The NAPSI score of a fingernail is the sum of scores in fingernail bed and fingernail matrix from each quadrant (maximum of 8). Each fingernail is evaluated, and the sum of all the fingernails is the total NAPSI score (range, 0-80), usually indicated as NAPSI score.	For each fingernail, if either bed or matrix score is missing or not done, the score for that finger is missing. If <50% of the finger scores from 10 fingers are missing, the imputation will be performed by using the average score of the remaining fingernails. If $\geq 50\%$ of the finger scores are missing, the NAPSI score will be left as missing.
		NAPSI score = 0	Calculated as: observed NAPSI – baseline NAPSI	Missing if baseline or observed value is missing
		NAPSI score = 0	A NAPSI response is defined as a NAPSI score of 0, which is also referred to as nail clearance.	Missing if NAPSI score is missing

Measure	Description	Variable	Derivation/Comment	Imputation Approach if with Missing Components

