PPASI	Palmoplantar Psoriasis Area and Severity Index (PPASI): will be used if the patient has palmoplantar psoriasis at baseline. Both palms and soles on each hand and foot will be individually assessed for erythema, induration, desquamation and percentage of area affected as follows: Erythema (E), Induration (I) and Desquamation (D): 0 = None 1 = Slight 2 = Moderate 3 = Severe 4 = Very Severe Percent of Palm and Sole Area Covered: 0 = None 1 = <10% 2 = 10 – 29% 3 = 30 – 49% 4 = 50 – 69% 5 = 70 – 89% 6 = 90 – 100%	PPASI score	The PPASI score is a composite score derived from the sum scores for E, I, and D multiplied by a score for the extent of palm and sole area involvement. The range is 0-72. $PPASI = 0.2(E_{rp} + I_{rp} + D_{rp})A_{rp} + 0.2(E_{lp} + I_{lp} + D_{lp})A_{lp} + 0.3(E_{rs} + I_{rs} + D_{rs})A_{rs} + 0.3(E_{ls} + I_{ls} + D_{ls})A_{ls}$ Where, E _{rp} , E _{lp} , E _{rs} , E _{ls} = Erythema score of plaques on the right palm (rp), left palm (lp), right sole (rs), left sole (ls), scored 0-4 respectively; I _{rp} , I _{lp} , I _{rs} , I _{ls} = Induration score of plaques on the right palm (rp), left palm (lp), right sole (rs), left sole (ls), scored 0-4 respectively; D _{rp} , D _{lp} , D _{rs} , D _{ls} = Desquamation score of plaques on the right palm (rp), left palm (lp), right sole (rs), left sole (ls), scored 0-4 respectively; A _{rp} , A _{lp} , A _{rs} , A _{ls} = numerical value translation of % area covered for the right palm, left palm, right sole, and left sole, respectively.	If any individual score is missing, the PPASI score will not be calculated, hence missing.
		PPASI change from baseline	Calculated as: observed PPASI – baseline PPASI	Missing if baseline or observed value is missing
		PPASI percent improvement from baseline	Calculated as: $Percent\ improvement\ from\ baseline = 100 \times \frac{Baseline\ PPASI - Observed\ PPASI}{Baseline\ PPASI}$ If a patient has experienced an improvement, this measure will be positive. If a patient has experienced a worsening in the condition, this measure will be negative.	Missing if baseline or observed value is missing
		PPASI 50	At least a 50% improvement in PPASI score from baseline	Missing if baseline or observed value is missing

Measure	Description	Variable	Derivation/Comment	Imputation Approach if with Missing Components
		PPASI 75	at least a 75% improvement in PPASI score from baseline	Missing if baseline or observed value is missing

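### The NAPSI missing-nail rule can count a patient with recorded nail disease as having nail clearance, and nonresponder imputation does not catch it

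*SAP*

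**What the plan says.** SAP section 6.11, Table AMAJ.6.5, scores each fingernail as bed (0-4) plus matrix (0-4) and sums ten nails to a total of 0-80. For incomplete data it gives three rules:

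- At nail level: "For each fingernail, if either bed or matrix score is missing or not done, the score for that finger is missing".
- At patient level: "If <50% of the finger scores from 10 fingers are missing, the imputation will be performed by using the average score of the remaining fingernails".
- At 50% or more, the total is not filled: "of the finger scores are missing, the NAPSI score will be left as missing".

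The responder endpoint is then built on that total: "A NAPSI response is defined as a NAPSI score of 0, which is also referred to as nail clearance". Its own missing-data entry makes it missing only when the NAPSI score is missing.

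Table AMAJ.6.6 analyses NAPSI = 0 by CMH with NRI in ITT patients who had nail involvement at baseline. Under SAP 6.3.1, NRI makes a patient a nonresponder when the response criterion is not met or the response is missing at the visit.

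The other skin indices in Table AMAJ.6.5 follow a stricter rule. For PPASI: "If any individual score is missing, the PPASI score will not be calculated, hence missing". PASI and PSSI have the same rule.

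**The concern.** The two filling steps act in sequence. The first discards a recorded bed or matrix score because its partner is missing. The second replaces the nail with the mean of nails that may all be 0. A patient whose record shows nail disease at the visit can then be reported as cleared.

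This is more than a debatable imputation. Neither component can be negative, so a single recorded value above 0 already settles that the total is not 0, whatever the missing partner would have been. What is at stake is the credibility of the reported nail clearance rate.

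**Working it through.** **Inputs, all from the NAPSI rows of Table AMAJ.6.5:** ten nails; bed 0-4 and matrix 0-4; nail missing if either part is missing; filled with the mean of the others if fewer than 5 of 10 are missing; response if total = 0.

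**Check of the plan's figure.** Maximum total = 10 x (4 + 4) = 80, which matches the stated range.

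**Half-scored nails.** Let h nails have a recorded bed score b above 0 and no matrix score, and let the other 10 - h nails be fully scored at 0.

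- Share missing = h/10, which is below 50% for h = 1 to 4.
- Fill value = 0/(10 - h) = 0.
- Total under the SAP = 0 + h x 0 = 0.
- Lowest total the recorded data allow = h x b.

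| h | Recorded points, b = 1 | Recorded points, b = 4 | SAP total | Classification |
|---|---|---|---|---|
| 1 | 1 | 4 | 0 | clear |
| 2 | 2 | 8 | 0 | clear |
| 3 | 3 | 12 | 0 | clear |
| 4 | 4 | 16 | 0 | clear |
| 5 | 5 | 20 | missing | NRI nonresponder |

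So up to four nails and 4 x 4 = 16 recorded points can be classed as clear. One more incomplete nail turns the same patient into a nonresponder.

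**Does NRI catch it?** It has two triggers. The criterion (total = 0) is met, and the total is not missing. Neither trigger fires.

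**Wholly unassessed nails.** The arithmetic is the same: if the assessed nails are all 0, up to four unassessed nails are filled with 0. Here the data do not contradict clearance, but they cannot establish it. As an illustration, assume that the u unassessed nails are a random subset and that d nails are diseased. The chance that every diseased nail is among the unassessed ones is C(10-d, u-d)/C(10, u):

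- d = 1: u/10, that is 10%, 20%, 30% and 40% for u = 1 to 4.
- d = 2, u = 4: 28/210 = 13.3%.
- d = 3, u = 4: 7/210 = 3.3%.

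**Direction within a patient.** The filled total is 0 exactly when all fully scored nails are 0. A truly clear patient always satisfies that, so the fill cannot turn a clear patient into a non-clear one. It can overstate the total: one nail with a recorded 0 and a missing partner, with the other nine at 4, is filled with 4 to give 40. That patient was not clear anyway. On the binary endpoint, then, the fill errs only towards clearance.

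**The case against.** **Other endpoints also tolerate gaps.** A reader might infer that the NAPSI rule breaks a principle applied to every other clearance endpoint. The SAP does not support that. A weekly PSS score needs only 4 of 7 diary days, the DLQI total is missing only when two or more questions are missing, and some QIDS-SR16 domains are missing only when all their items are. Table AMAJ.6.5 sets component rules measure by measure. The fair contrast is with PASI, PSSI and PPASI only.

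**The change score.** A reader might also infer that change in NAPSI, listed in Table AMAJ.4.1 as "Change from baseline in NAPSI total score in patients with fingernail involvement at baseline", is biased towards improvement. Take two nails at 8, eight at 0, and one nail missing. Losing a diseased nail gives 8 x 10/9 = 8.89 against a true 16; losing an unaffected nail gives 16 x 10/9 = 17.78. If the missing nail is random, the expected total is 0.2 x 8.89 + 0.8 x 17.78 = 16.0. The fill adds noise but no bias under that assumption, so no point is made against the change score.

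**Rarity and reach.** The misclassification by half-scored nails needs a recorded value above 0, at most four incomplete nails, and 0 on every fully scored nail. The documents give no frequency for this. The percentages above are conditional illustrations, not error rates for the endpoint. The rule is the same in every arm. NAPSI = 0 is not among the endpoints in Table AMAJ.4.1, and the graphical procedure in SAP 6.5 covers only primary and major secondary endpoints.

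All of this limits the weight of the point. None of it answers the core: the rule as written assigns a score of 0 to patients whose recorded data exclude it.

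**Conclusion.** The point holds and is minor. Followed literally, Table AMAJ.6.5 can report nail clearance for a patient with up to four half-scored nails and up to 16 recorded points, and NRI does not intervene. That classification is wrong on the recorded data alone and needs no assumption about the missing parts. Counting up to four wholly unassessed nails as clear is a weaker matter: it is out of line with PASI, PSSI and PPASI, but it is a convention rather than a contradiction.

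The effect on the reported clearance rate cannot be estimated, because the number of incomplete nail assessments is not given. A reader might suppose that the rule favours mirikizumab. The documents do not show this: the rule applies equally to all arms, and the direction of any bias between them is undetermined. No primary or major secondary conclusion depends on this endpoint.

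**What to change.** Add two statements to the NAPSI score = 0 row of Table AMAJ.6.5:

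1. The response is not met if any bed or matrix score recorded at that visit is above 0.
2. A filled total cannot establish clearance: if any of the ten nails lacks a bed or matrix score, the response is missing, and the patient is a nonresponder under NRI.

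The first statement corrects the error. The second brings the endpoint into line with PASI, PSSI and PPASI. If the second is judged too strict, the first alone still removes the contradiction with recorded data. The rule for the NAPSI total and its change from baseline ("the imputation will be performed by using the average score of the remaining fingernails") can stay as it is.

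The cost is a few words and one change to the derivation, using data already collected. The clearance rate may fall slightly, because a patient with one unassessed nail and nine clear ones would count as a nonresponder.

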PASI	
Psoriasis Area and Severity Index (PASI): combines assessments of the extent of body surface involvement in 4 anatomical regions (head and neck, trunk, arms, and legs) and the severity of scaling (S), redness (R), and plaque induration/infiltration (thickness, T) in each region, yielding an overall score of 0 for no psoriasis to 72 for the most severe disease (Fredriksson and Pettersson 1978). Severity is rated for each index (R, S, T) on a 0-4 scale (0 for no involvement up to 4 for very severe involvement):
 
0 = none 1 = slight 2 = moderate 3 = severe 4 = very severe
 
The body is divided into 4 anatomical regions comprising the head (h), upper limb (u), trunk (t), and lower limb (l). In each of these areas, the fraction of total body surface area affected is graded on a 0-6 scale (0 for no involvement; up to 6 for 90% - 100% involvement):
 
0 = 0% (clear) 1 = >0% to <10% 2 = 10% to <30% 3 = 30% to <50% 4 = 50% to <70% 5 = 70% to <90%
	PASI score	
The composite PASI score is calculated by multiplying the sum of the individual severity scores for each area by the weighted area-of-involvement score for that respective area, and then summing the 4 resulting quantities as follows:
 $PASI = 0.1(R_h + T_h + S_h)A_h + 0.2(R_u + T_u + S_u)A_u + 0.3(R_t + T_t + S_t)A_t + 0.4(R_l + T_l + S_l)A_l$ 
Where,
 
R_h, R_u, R_t, R_l = redness score of plaques on the head, upper limb, trunk, and lower limb, scored 0-4 respectively; T_h, T_u, T_t, T_l = thickness score of plaques on the head, upper limb, trunk, and lower limb, scored 0-4 respectively; S_h, S_u, S_t, S_l = scaliness score of plaques on the head, upper limb, trunk, and lower limb, scored 0-4 respectively; A_h, A_u, A_t, A_l = numerical value translation of % area of psoriatic involvement score for the head, upper limb, trunk, and lower limb, respectively.
 
PASI scores are treated as a continuous score, with 0.1 increments within these values.
	If any individual score is missing, the PASI score will not be calculated, hence missing
		PASI change from baseline	Calculated as: observed PASI – baseline PASI	Missing if baseline or observed value is missing

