		DLQI daily activities domain	Sum of responses of questions #3 and #4: #3. How much has your skin interfered with you going shopping or looking after your home or garden? #4. How much has your skin influenced the clothes you wear?	If 1 question in a domain is missing, that domain is missing.
		DLQI leisure domain	Sum of responses of questions #5 and #6: #5. How much has your skin affected any social or leisure activities? #6. How much has your skin make it difficult for you to do any sport?	If 1 question in a domain is missing, that domain is missing.
		DLQI work and school domain	Sum of responses of questions question #7A and #7B: #7A. Has your skin prevented you from working or studying? #7B. If No: how much has your skin been a problem at work or studying?	If the answer to question #7A is missing, this domain is missing. If #7A is No, and #7B is missing, this domain is missing.
		DLQI personal relationships domain	Sum of responses of questions #8 and #9: #8. How much has your skin created problems with your partner or any of your close friends or relatives? #9. How much has your skin caused any sexual difficulties?	If 1 question in a domain is missing, that domain is missing.
		DLQI treatment domain	Response of question #10: #10. How much of a problem has the treatment for your skin been, for example by making your home messy, or by taking up time?	If 1 question in a domain is missing, that domain is missing.
WPAI-PSO	The Work Productivity and Activity Impairment-Psoriasis (WPAI-PSO) Questionnaire is a patient-reported instrument developed to measure the	Employment Status	Yes/No	Missing if question is missing
		Absenteeism Score (%)	$\frac{Q2}{(Q2 + Q4)} \times 100$	Missing if Q2 or Q4 are missing. Also missing if

Measure	Description	Variable	Derivation/Comment	Imputation Approach if with Missing Components
	impact on work productivity and regular activities attributable to a specific health problem (psoriasis). It contains 6 items that measure: 1) employment for pay status, 2) hours missed from work due to the psoriasis, 3) hours missed from work for other reasons, 4) hours actually worked, 5) degree of health-affected productivity while working, and 6) degree of health affected productivity in regular unpaid activities. Greater scores indicate greater impairment (Reilly Associates Health Outcomes Research [WWW]).			Employment Status is No.

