		Presenteeism Score (%)	$\frac{Q5}{10} \times 100$	Missing if Q5 is missing. Also missing if Employment Status is No.
		Work Productivity Loss Score (%)	$\left[\frac{Q2}{Q2 + Q4} + \left(1 - \frac{Q2}{Q2 + Q4} \right) \frac{Q5}{10} \right] \times 100$	Missing if Q2, Q4, or Q5 is missing. Also missing if Employment Status is No.
		Activity Impairment Score (%)	$\frac{Q6}{10} \times 100$	Missing if Q6 is missing. May still be present and nonmissing if patient is unemployed.
SF-36	The SF-36 Version 2 is a 36-item, patient-completed measure designed to be a short, multipurpose assessment of health (The SF Community – SF-36 Health Survey Update). The summary scores range from 0-100, with higher scores indicating better levels of function and/or better health. Items are answered on Likert scales of varying lengths. The SF-36 comprises 8 domain scores and 2 overarching component scores. SF-36 domain scores are: (1) Physical functioning, (2) Role-physical, (3) Role-emotional, (4) bodily pain, (5) vitality, (6) social functioning, (7) mental health, and (8) general health. The component scores are: (1) the Physical Component Summary (PCS) and (2) Mental Component Summary (MCS).	SF-36 Domain scores and SF-36 Component Scores	Per copyright owner, the Quality Metric Health Outcomes™ Scoring Software will be used to derive SF-36 domain and component scores. After data quality-controls, the SF-36 software will recalibrate the item-level responses for calculation of the domain and component scores. These raw scores will be transformed into the domain scores (t-scores) using the 1-week recall period. This entails exporting the patient data in a CSV or tab-delimited file for import, generation of the SF-36 scores and reports, and export of the calculated scores in a CSV or tab-delimited file for integration into SDTM/ADAM datasets.	Missing data handling offered by SF-36 software will be used. “Maximum Data Recovery” will be selected for Missing Score Estimator in the software.
		SF-36 change from baseline for domain and component	Calculated as: observed SF-36 score – baseline SF-36 score	Missing if baseline or observed value is missing

Measure	Description	Variable	Derivation/Comment	Imputation Approach if with Missing Components
	The SF-36 acute version will be used, which has a 1 week recall period. Responder Definitions were determined in the user's manual (Maruish 2011).	scores		

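### WPAI-PSO Work Productivity Loss is set to missing when item Q5 is blank, even when no hours were worked because of psoriasis and the formula already fixes the score at 100%

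*SAP*

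**What the plan says.** All the derivation rules are in SAP Section 6.11, Table AMAJ.6.5.

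- **Items.** The WPAI-PSO records "2) hours missed from work due to the psoriasis, 3) hours missed from work for other reasons", followed by "4) hours actually worked, 5) degree of health-affected productivity while working". Item Q3 enters none of the scores.
- **Absenteeism.** This is Q2/(Q2 + Q4) × 100. Its rule begins "Missing if Q2 or Q4 are missing. Also missing if" and goes on to patients who are not employed. Q5 plays no part.
- **Work Productivity Loss.** This is [Q2/(Q2 + Q4) + (1 − Q2/(Q2 + Q4)) × Q5/10] × 100, with the rule "Missing if Q2, Q4, or Q5 is missing. Also missing if Employment Status is No". No exception is made for Q4 = 0.
- **DLQI, for comparison.** The same table accepts a blank on question 7B when the answer to 7A makes 7B inapplicable.

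Table AMAJ.6.6 analyses the change from baseline in the WPAI-PSO scores among patients employed at baseline. It uses ANCOVA with mBOCF at the last induction visit, and MMRM plus ANCOVA with mBOCF over the combined periods. Table AMAJ.4.1 lists the WPAI-PSO scores as other secondary endpoints. The graphical procedure in Section 6.5 covers only primary and major secondary endpoints.

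**The concern.** A missing-component rule should withhold a score when the missing item could change it. Here the rule also withholds a score that the item cannot change. The patients concerned are employed but worked no hours because of psoriasis, which is the worst outcome the scale can record. Item Q5, "5) degree of health-affected productivity while working", has no natural answer for someone who did not work, so a blank is plausible in just these patients.

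If Q5 is blank, missingness is tied to the value itself.

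- **At baseline.** No change score can be formed, and the baseline covariate is missing. Unless an earlier pre-dose score exists, a maximally impaired patient drops out of the Work Productivity Loss analysis.
- **After baseline.** mBOCF (Section 6.3.3) substitutes the last recorded value, which cannot exceed 100% and so is equal or more favourable. MMRM (Section 6.3.2) relies on correlation with the patient's other visits, which does not reliably recover a value that is missing because it is extreme.

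**Working it through.** The SAP states no numerical result for this score, so there is no figure to reproduce. The check evaluates the SAP's own formulas.

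**Inputs (Table AMAJ.6.5).** Q2 = hours missed because of psoriasis, Q4 = hours worked, Q5 = rating from 0 to 10. Write A = Q2/(Q2 + Q4). Then Absenteeism = 100 × A and Loss = 100 × [A + (1 − A) × Q5/10].

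**Step 1: Q4 = 0 and Q2 > 0.** A = Q2/(Q2 + 0) = 1, so Loss = 100 × [1 + 0 × Q5/10] = 100%. Evaluation with Q2 = 1, 8 and 40 hours, over every Q5 from 0 to 10, gives 100% each time. Q5 is not needed.

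**Step 2: Q4 > 0.** Take Q2 = 8 and Q4 = 32, so A = 8/40 = 0.2.

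| Q5 | Loss |
|---|---|
| 0 | 100 × (0.2 + 0.8 × 0) = 20% |
| 5 | 100 × (0.2 + 0.8 × 0.5) = 60% |
| 10 | 100 × (0.2 + 0.8 × 1) = 100% |

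A blank Q5 leaves Loss anywhere from 20% to 100%. Here the present rule is right.

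**Step 3: Q2 = Q4 = 0.** A = 0/0, which is undefined. This arises, for example, when all hours were missed for other reasons (Q3). Neither Absenteeism nor Loss can be computed, so missing is correct. The table does not say so, since neither item is itself missing.

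**Step 4: consistency within the table.** Loss − Absenteeism = 100 × (1 − A) × Q5/10, which is never negative. Loss therefore cannot fall below Absenteeism. With Q4 = 0, Q2 > 0 and Q5 blank, the rules score Absenteeism at 100% and declare Loss missing, although Loss can then only be 100%.

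**Step 5: bound on the effect after baseline.** Let a fraction f of an arm's patients be affected at a visit. If mBOCF carries a value v (0 to 100) for such a patient, the error is 100 − v, so the arm's raw mean is too low by f × (100 − mean v), at most 100 × f. If these patients are instead excluded and the others have mean m, the shortfall is f × (100 − m), again at most 100 × f. The documents give no f. With assumed values of 1%, 2% and 5%, the ceilings are 1, 2 and 5 percentage points in one arm. These are upper limits for a raw arm mean, not estimates of the adjusted treatment difference.

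**The case against.** The strongest reply is that the rule does not mention zero hours. It acts only when an item is blank. A patient with Q4 = 0, Q2 > 0 and any recorded Q5 gets 100% under the present text, and no skip instruction for Q5 is documented. That is correct and it limits the point: a blank Q5 is plausible from the wording of the item, but not established.

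Other parts of the reply also stand. Absenteeism still records the lost week. The endpoint is outside the multiplicity procedure. If the lost values fell mainly in the placebo arm after baseline, the bias would run against mirikizumab. None of this gives a reason to discard a score that the formula fixes.

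A reader might make two stronger inferences, which the documents do not support.

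- **Every patient with zero hours is a lost 100%.** This fails when Q5 is recorded, and when Q2 is also 0, because the score is then undefined.
- **The same fault reaches the primary endpoint through PASI, and also PSSI and PPASI.** The PASI rule is "If any individual score is missing, the PASI score will not be calculated, hence missing", and a region with area score 0 does contribute nothing, whatever its severity items. But all three scales provide a severity score of 0 for clear skin, so a clear region has an answer to enter. Nothing in the documents shows that those items are, or can be, left blank. A blank there may also signal an incomplete assessment, for which treating the score as missing is defensible.

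**Conclusion.** The point holds for one defined case: an employed patient with Q4 = 0, Q2 > 0 and Q5 blank. There the Work Productivity Loss rule discards a score that its own formula sets at 100%, and it disagrees with the Absenteeism rule beside it. This follows from the algebra alone. Its practical weight rests on an assumption that the documents neither confirm nor exclude, namely that some patients who worked no hours leave Q5 blank.

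The consequence is confined to an other secondary endpoint. Losses at baseline occur before treatment starts, so they mainly change who is analysed. Losses after baseline flatter whichever arm has more of them. Neither the size nor the direction of a between-arm bias can be determined from the documents, and no effect on a primary or major secondary endpoint is shown. This is a small correction to a derivation rule.

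**What to change.** In Table AMAJ.6.5, replace the Work Productivity Loss rule for employed patients with three cases:

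1. If Q4 = 0 and Q2 > 0, set Work Productivity Loss to 100% regardless of Q5.
2. If Q2 = Q4 = 0, set Work Productivity Loss to missing, because the ratio is 0/0. State the same for Absenteeism.
3. Otherwise keep the present rule.

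Patients who are not employed stay missing, as now. The cost is a few lines in one table and one branch in the derivation program. It needs no new data, imputes nothing that the formula does not already determine, and leaves the primary and major secondary analyses unchanged. It should be settled before treatment codes are known to the study team, so that it is not a choice made after seeing results.
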